6.8.2 Concomitant medications

Information regarding concomitant medications (prescription medications, over-the-counter medications, herbal and naturopathic medications, etc.) will be collected at the start of screening and at each follow-up visit.

In general, participants should continue with the same medications and regimens they were taking at the time of study enrollment. The doses of these concomitant medications should be kept as stable as possible during the study. In general, medications that the investigator considers appropriate for the treatment of any intercurrent illness or preexisting condition that is not on the list of prohibited medications or that does not constitute an exclusion criterion for participation in this study will be permitted.

7. RISKS AND PRECAUTIONS

7.1 Precautions

The investigator must be aware of the administration of investigational drugs in the following situations:

- Depression or psychiatric conditions: These participants must be carefully evaluated, and participation may be permitted if there is no evidence of uncontrolled symptoms, worsening, or major depression. Participants with severe psychiatric conditions should not participate in this research program.
- Participants should eat after taking the medications. It is not recommended to take them on an empty stomach or to fast immediately after taking the medications.
- Participants with a history of seizures may participate if they have not occurred in the past 60 days and are stable and under pharmacological control.

7.2 Adverse Reactions

7.2.1 Fluvoxamine

Most adverse reactions reported in clinical studies conducted with fluvoxamine are gastrointestinal symptoms, generally of mild intensity (nausea, dyspepsia, mild diarrhea, abdominal pain). Other adverse reactions: agitation, anxiety, insomnia, headache, anorexia, palpitations, hyperhidrosis, malaise, QT interval prolongation ($QTcF \geq 450$ msec). Aside from gastrointestinal symptoms, the occurrence of other symptoms is uncommon in treatments lasting less than 30 days.

7.2.2 Metformin

Most adverse reactions reported in clinical studies conducted with metformin are self-limiting and resolve upon discontinuation of the medication or with non-pharmacological measures. Common reactions to metformin use include: heartburn, stomach pain, nausea or vomiting, bloating, gas, diarrhea, constipation, weight loss, headache, and an unpleasant metallic taste in the mouth.

8. STUDY PROCEDURES

8.1 Screening Procedures

Before any specific study procedure, the participant will receive an explanation of all study procedures and must date and sign an informed consent form (ICF) approved by a Research Ethics Committee (REC). The screening visit will be conducted (1) at Primary Health Care Units / Outpatient Clinics.

Eligible participants will be identified during the clinical consultation. Participants diagnosed with long COVID-19 will be invited to learn about the research project. If they express interest, they will be referred to a designated and trained research team member who will present the proposed research program and provide the Informed Consent Form (ICF), which will be presented in accordance with current regulatory standards for clinical research. Research procedures will only begin if participants express interest in participating in the research program and sign the ICF. During the screening visit, participants will receive a unique participant number, which will be generated during the registration of the screening visit in the IWRS.

Participants are first screened to identify those who meet the eligibility criteria. When a participant meets all eligibility criteria, they begin the baseline visit phase.

The participant signs the TCLE
 Review of eligibility criteria.
 Pregnancy test for women of childbearing age.
 Completion and scoring of the FSS.
 Other procedures scheduled for the visit.

8.2 Day-1 procedures ation / randomization

The procedures performed prior to administration of the investigational drug and randomization must be performed immediately after confirmation of eligibility criteria and obtaining informed consent for participation in the study. The following procedures will be performed during this visit:

- Registration in the IWRS.
- Participant demographic data.

- Medical history, including elective surgical procedures scheduled within 60 days of randomization;
- Comorbidities and risk factors.
- Concomitant medications.
- Physical examination findings.
- Vital signs (including temperature, heart rate, respiratory rate, and oxygen saturation in room air).
- Details of your medical history of COVID-19.
- Randomization and administration of the first dose of the investigational product/placebo.
- Dispensing of the investigational product/placebo and instructions regarding it.
- Instructions regarding subsequent visits.

Participants will receive their first dose of the investigational medical product (fluvoxamine, metformin, or corresponding placebo) at the research center before being discharged home. They will be instructed to take the medications twice daily for 60 days.

8.3 Procedures during participant follow-up

In-person follow-up visits will take place on days 7, 30, 60, 90, and 180, all at intervals of ± 5 days, following randomization. Participants will be asked to complete the FSS and the EQ-5D-5L 30 days, 60 days, and 90 days after randomization. Additionally, on days 7, 30, 60, and 90, the local research team will verify the participant's status regarding the outcomes of all-cause mortality and unplanned hospitalization for all causes. The research team will collect data on adherence to the experimental product and the placebo (Days 7, 30, and 60). The research team will also document concomitant medications. Participants will be monitored for adverse events and laboratory abnormalities (if they have undergone tests) at each visit.

During the post-study period (visits on days 90 and 180 after randomization), symptoms present at the Day 60 visit will be recorded, as well as new events and symptoms. The D90 and D180 questionnaires (FSS Scale and EQ-5D-5L) will be administered.

The above data will be collected directly from the participant, from the participant's medical record, or from the healthcare professional(s) responsible for treatment if it is impossible to collect the data directly from the participant. If a participant is unable to return to the health center for a follow-up visit, the research team may contact them and conduct the visit via telephone, social media, and/or telemedicine. Data may also be collected through valid electronic communication methods.

8.4 Procedures for Unscheduled Visits

An unscheduled visit may occur at the researcher's discretion or due to the patient's need and may take place during the treatment period up to the final study visit. During an unscheduled visit at any stage of the study, the following activities will be performed if conducted via telephone:

- Assessment of the reason for the unscheduled visit and determination of the course of action.
- Assessment of adverse events.
- Documentation of concomitant medications.
- Adherence to the investigational product/placebo.

Any other study assessments may be performed at the investigator's discretion during an unscheduled visit. In the event of clinical progression of complications expected for long COVID-19, related adverse events will be considered as expected for the clinical condition presented.

8.5 Procedures for early discontinuation of treatment/study withdrawal

For participants who withdraw prematurely from the study (before the Day 90 visit), the center must make every effort to ensure that the participant completes the follow-up visit, which must be conducted on the day of withdrawal or as soon as possible after withdrawal. The assessments conducted at the end-of-study visit must be the same as those for the Day 90 visit.

Participation in the study implies agreement to the proposed post-study period, which consists of two visits (conducted via telephone, social media, or telemedicine), one to be conducted on Day₉₀(30 days) and the other on Day₁₈₀(120 days) after the end of the therapeutic intervention phase.

9 STUDY ASSESSMENTS AND PROCEDURES

9.1 Laboratory Tests

In women of childbearing age, a pregnancy test is planned, and the biological material to be used is urine or serum. Laboratory tests may be performed to investigate adverse events or changes for which the researcher deems laboratory evaluations necessary, always with the participant's safety and well-being in mind.

9.2 Vital signs

The following vital signs data will be collected:

Temperature

Heart rate

Respiratory rate

Arterial oxygen saturation using a digital oximeter.

Weight and height (reported by the patient)

Respiratory rate will be measured by digital oximetry or physical examination (vital signs).

9.3 Physical Examination

The researcher will perform a brief physical assessment of the participant and document relevant findings in the participants' medical records.

9.4 *-reported outcomes*

The patient-reported outcome questionnaires (FSS and EQ-5D-5L) will be completed by participants at each visit, always as the first activity of the visit. Study coordinators will review the participant's responses immediately after the participant completes the questionnaires to ensure that all questions are answered.

The FSS questionnaire is a validated 9-item scale that measures the severity of fatigue and its effect on an individual's activities and lifestyle, using a 7-point Likert scale (1 = strongly disagree and 7 = strongly agree). The questionnaire asks the individual to rate the severity of fatigue over the past week. A low score indicates that the individual disagrees with the statement, and a high score indicates that the individual agrees with the statement. The response options selected for each of the 9 statements are summed, and the sum is divided by 9 (the number of questions) to obtain the

final mean score. The minimum average score is 1, and the maximum average score is 7. A score below 4 indicates that participants are not experiencing clinically relevant fatigue, which is considered an exclusion criterion for participation in the study. The Fatigue Severity Scale is commonly used in participants diagnosed with arthritis, fibromyalgia, multiple sclerosis, chronic fatigue syndrome, Parkinson's disease, stroke, and COVID-19. The validity and reliability of the questionnaire have been evaluated in different populations, including those studied following COVID-19.

The EQ-5D-5L is used globally as a generic measure of health status. The EQ-5D-5L descriptive system includes five dimensions: mobility, self-care, usual activities, pain/discomfort, and anxiety/depression. Each dimension has five levels: no problems, slight problems, moderate problems, severe problems, and extreme problems. Participants are also asked about their health status by checking the box next to the most appropriate statement in each of the five dimensions. This results in a single-digit number that expresses the selected level for that dimension. The digits from the five dimensions can be combined into a 5-digit number that describes the patient's health status. The EQ visual analog scale records the patient's self-assessment of health on a vertical visual analog scale, where the endpoints are labeled "The best health you can imagine" and "The worst health you can imagine." This can be used as a quantitative measure of health outcomes that reflect the patient's own judgment. The EQ-5D-5L is widely validated, and its applicability is recommended by regulatory agencies (FDA, EMA, and ANVISA).

9.5 Collection of Additional Data

The research team will also collect data on adherence to the investigational medical product. The research team will also document concomitant medications. Participants will be monitored for adverse events and laboratory abnormalities in tests performed for other purposes at each visit.

9.6 Contraception in women of childbearing potential

For women of childbearing potential, a urine or serum pregnancy test will be performed at the screening visit. A pregnancy test will be performed on all women of childbearing potential (childbearing potential being defined in this protocol as at least one menstrual period occurring in the past 12 months in women aged 18 to 55 years). Any pregnancy s during the treatment phase of the study will be monitored until delivery to assess potential complications and adverse events.

10 EVALUATION, RECORDING, AND REPORTING OF ADVERSE EVENTS

10.1 *Definition of Adverse Events*

²²⁸An adverse event is any unfavorable medical occurrence experienced by a patient or clinical trial participant who has received a drug and that does not necessarily have a causal relationship with that treatment. Therefore, an ADE may be any unfavorable and unintended sign (including an abnormal laboratory finding), symptom, or illness temporarily related to the use of an (experimental) drug, whether or not it is related to the (experimental) drug. This includes:

- (1) Any new clinical condition, sign, or symptom, clinically significant physical examination abnormality, or newly diagnosed event occurring during the ADR reporting period, including signs or symptoms associated with an underlying condition that was not present prior to the ADR reporting period;
- (2) A preexisting condition that has worsened in severity or frequency or changed in character after the participant signed the RCT during the ADR reporting period; and
- (3) Complications that occur as a result of interventions required by the protocol. An ADE may arise from any use of the investigational drug (e.g., off-label use, use in combination with another drug) and from any route of administration, formulation, or dose, including an overdose. Any side effects, harm, toxicity, or hypersensitivity reactions that may occur in a participant in this clinical trial may also be considered AEs.

For the purposes of this protocol, events that will not be considered AEs include:

- Fluctuating signs or symptoms expected from a pre-existing medical condition (e.g., tremor in a participant with Parkinson's disease; migraine episodes) that did not worsen in severity or frequency or change in character during the ADE reporting period;
- Surgeries or medical procedures are not AEs; however, the clinical condition (new or worsened) that led to the surgery or medical procedure is the reported AE (e.g., for appendicitis resulting in an appendectomy, the appendicitis should be reported as the AE);
- Overdose without clinical signs or symptoms.

10.2 *Adverse Event Reporting Period*

AEs, including serious adverse events (SAEs), will be collected throughout the study period, from the time the participant signs the WIC until the EoS visit. All AEs still present at the time of study completion will be monitored by the investigator through contact with the participant until resolution or stabilization, or until the participant is lost to follow-up and can no longer be contacted. The outcome must be documented in the participant's source documents. The investigator must report

all SAEs that occur after the reporting period specified in the protocol if, in the investigator's judgment, there is a reasonable possibility that the SAE is related to the investigational product or any study procedure.

10.3 Identification of Adverse Events

If a participant reports an adverse event, it is the investigator's responsibility to obtain sufficient information to assess causality. This may require additional laboratory tests, a physical examination, telephone contact, etc.

To avoid bias in the collection of AEs, participants should be asked to answer a neutral question, such as "How are you feeling?" It is also important to ask the participant, in a non-leading manner, about changes in their health or use of concomitant medications since the last visit. This information should be collected prior to the assessments at all study visits. In addition, any symptoms/conditions reported during the assessments and considered clinically significant by the investigator will be evaluated as AEs.

10.4 Adverse Event Assessment

10.4.1 Intensity/ Severity

The medical assessment of intensity will be determined using the following definitions:

Mild: The AE is easily tolerated and does not affect usual activities.

Moderate: The AE affects daily activities, but the participant is still able to perform them.

Severe: The AE is incapacitating, and the participant cannot work or perform their usual activities.

A new event will be documented whenever the intensity of an event changes. It is important to note the distinctions between serious AEs and serious adverse events (SAEs). Severity is a classification of the intensity of a specific event (such as mild, moderate, severe); however, the event itself may be of relatively minor clinical importance (such as a severe headache).

A SAE, however, is an AE that meets any of the specified regulatory criteria required for severity designation (for example, a headache may be severe [significantly affecting the participant's usual functions], but would not be classified as severe unless it met any of the criteria for SAEs).

10.4.2 Causality and Reporting

The investigator will provide a causality assessment for all AEs using their best clinical judgment based on the available medical information regarding the event being reported. The causality assessment will be reevaluated as new information becomes available. If the investigator's causality assessment is not reported, the event will be considered "related" until such information is received. Each investigator will assess the degree to which the ADR is related to the investigational drugs using the following definitions:

Unrelated: There is no reasonable possibility that the investigational product caused or contributed to the ADE.

- The event is related to an etiology other than the investigational drug, such as an underlying disease, study-unrelated procedures, concomitant medication, or the subject's clinical condition.
- The timing of the ADE is not reasonably related to the administration of the investigational drug.

Related: There is a reasonable possibility that the investigational product caused or contributed to the AE.

- There is no compatible temporal association between the event and the administration of the investigational drug.
- Is there a biologically plausible mechanism by which the study treatment could have caused or contributed to the ADE?
- The event improves or resolves after discontinuation of the study drug without the initiation of any specific treatment for the event (withdrawal from exposure) and/or the event recurs or worsens after reintroduction of the study therapy.
- The event cannot reasonably be attributed to a concomitant or underlying disease or to other medications or procedures.

For the purposes of causality assessment, "reasonable possibility" means that, based on the investigator's medical judgment regarding the available information, there are facts or arguments suggesting a positive causal relationship.

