10.6 Adverse drug reactions and reference safety information

10.6.1 Adverse drug reaction

An adverse drug reaction (ADR) is an undesirable and unintended response to a drug related to any administered dose. This definition implies a reasonable possibility of a causal relationship between the event and the investigational drug. This means that there are facts (evidence) or arguments suggesting a causal relationship.

Given that the investigational drugs have been commercially approved by ANVISA for decades, in this study only adverse reactions not yet described in ANVISA's drug dossier and assessed by the investigator as having a reasonable causal relationship with a drug (under investigation) will be considered ADRs. Thus, no reports of ADRs related to the drugs used in this study are expected.

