10.7.3 SUSARs

A suspected unexpected serious adverse reaction (SUSAR) is defined as any serious and unexpected adverse drug reaction (ADR).

For the purposes of this protocol, the occurrence of SUSARs is not expected, since the drugs were approved several years ago by ANVISA and have been used in hundreds of thousands of participants, and potential adverse reactions and/or idiosyncrasies are already well known to regulatory authorities.

The sponsor or investigator must notify the ethics committee and regulatory authorities of all SUSARs and other types of AEs (if applicable) in accordance with local safety requirements.

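### One of the four criteria for a Related adverse event (protocol section 10.4.2) is stated in the negative, so the same timing finding supports both Related and Unrelated

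*Protocol*

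**What the plan says.** Section 10.4.2 of the protocol requires a causality assessment for every adverse event and sets out two categories, each with a defining sentence and supporting bullets.

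- Related is defined by "Related: There is a reasonable possibility that the investigational product caused or contributed to the AE". Its four bullets concern timing, biological mechanism, the course after stopping or reintroducing the drug, and the absence of another explanation.
- The timing bullet under Related reads "There is no compatible temporal association between the event and the administration of the investigational drug".
- Unrelated has two bullets: another cause, and timing. The timing bullet reads "The timing of the ADE is not reasonably related to the administration of the investigational drug".
- The section closes by explaining a reasonable possibility as meaning that, in the investigator's medical judgment, "there are facts or arguments suggesting a positive causal relationship".
- There is a default for missing assessments: where the investigator's "causality assessment is not reported, the event will be considered" related until the information arrives.

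Other sections use the result. Section 10.6.1 says of an adverse drug reaction: "This definition implies a reasonable possibility of a causal relationship between the event and the investigational drug". Section 10.7.3 defines a SUSAR as a serious and unexpected adverse drug reaction. Sections 10.2 and 10.7.2 make the reporting of serious events found after the reporting period or after the study depend on a possible causal link.

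**The concern.** A missing temporal link is ordinarily a reason to doubt that a drug caused an event. Here it appears as a reason to call the event Related, and a few lines earlier as a reason to call it Unrelated. An investigator, monitor or auditor who goes to the list to settle a timing question finds support for either answer, with nothing to say which bullet governs.

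This is an operative definition, because investigators are told to use it for every event. A wrong Unrelated call can take an event out of the adverse drug reaction category and therefore out of SUSAR status. A wrong Related call can do the reverse. For serious events found late, timing relative to the last dose is a central part of the judgment, and timing is the criterion that is stated backwards.

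**Working it through.** No sample size, error rate or event count enters, so the check sets the texts side by side.

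**Step 1. Direction of each statement in section 10.4.2.**

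| Statement | Points towards |
|---|---|
| Defining sentence for Related | drug caused or contributed: correct direction |
| Related, bullet 1 (timing) | no temporal link: reversed |
| Related, bullet 2 (mechanism, phrased as a question) | plausible mechanism: correct direction |
| Related, bullet 3 (stopping and reintroducing the drug) | link with exposure: correct direction |
| Related, bullet 4 (no other explanation) | drug: correct direction |
| Unrelated, bullet 1 (other cause) | not the drug: correct direction |
| Unrelated, bullet 2 (timing) | no temporal link: correct direction |
| Closing definition of a reasonable possibility | positive causal evidence: correct direction |

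One of the four Related bullets is reversed, and it collides with one of the two Unrelated bullets.

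**Step 2. Conflict within Related.** Bullet 3 reads in part "The event improves or resolves after discontinuation of the study drug without the initiation of any specific treatment for the event" and goes on to recurrence or worsening on reintroduction. Both patterns describe an event that follows exposure in time, so they presuppose the temporal association that bullet 1 says is absent.

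**Step 3. Two hypothetical events.**

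- Event A starts soon after dosing begins, has a plausible mechanism and resolves on stopping. The defining sentence and bullets 2 and 3 say Related; bullet 1 is not met.
- Event B has timing that does not fit exposure. The Unrelated timing bullet is met, and so is Related bullet 1.

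Event A loses support that it should have. Event B gains support for Related that it should not have.

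**Step 4. Where the causality call is used.**

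- Adverse drug reactions (10.6.1): the event must be assessed as having a reasonable causal relationship and must not already be described in the ANVISA dossier.
- SUSARs (10.7.3): these inherit the call through the adverse drug reaction definition and are notified to the ethics committee and regulators.
- Serious events up to the 90-day visit (10.7.2): reported within 24 hours regardless of relationship, so this duty does not turn on the bullet.
- Serious events found later (10.2, 10.7.2): reported if considered possibly or causally related. Treatment ends at day 60, so the 90-day visit is 90 − 60 = 30 days after treatment, and the day-180 contact is 180 − 60 = 120 days after it, as section 8.5 also states.
- Planned analysis (summary table, 12.11): a descriptive account of adverse events by treatment group, with no count of related events named.

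**Step 5. Search for a correction.** No other section restates the timing criterion the right way round or says which of the two timing bullets prevails.

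**The case against.** The strongest reply is that the rule itself is sound. The defining sentence, three of the four Related bullets and the closing explanation all point the right way. The call rests on the investigator's clinical judgment and is revisited as information arrives. An experienced investigator will read the bullet as a slip, which is plausible: the neighbouring bullet has become a question, and parts of the protocol remain in Portuguese. That is an inference, and whether sites work from this English text cannot be seen. Most of this reply stands, and it limits the finding to a risk. It does not remove the contradiction: it leaves two opposed timing bullets in force, and the default to related helps only when no assessment is given, not when one is made on a wrong criterion.

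A reader might infer more: that if any single bullet suffices, every event without a temporal link becomes Related, and that if all four are needed, almost nothing can be Related. The section gives no counting rule. The bullets, one of them a question, read more naturally as prompts to judgment than as a scoring scheme, so neither consequence follows from the text.

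A reader might also want a size. The one nearby figure, 9% of the first 100 recruited participants dropping out for mild adverse effects (section 3.3.2), comes from a blinded analysis and is not a rate of drug-related events. Nor would an absence of SUSARs measure the harm, since section 10.7.3 expects none in any case.

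One qualification goes the other way. Section 10.7.1 removes expected reactions to the study drugs from the definition of a serious adverse event, so a relatedness judgment can enter before section 10.7.2 applies. That is a separate matter, and this point does not rest on it.

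**Conclusion.** The point holds in a limited form. One of four supporting criteria for Related is stated in the negative. It contradicts its own defining sentence and the criterion on stopping and reintroducing the drug, and it duplicates the Unrelated timing criterion. The consequence is a risk of inconsistent or wrong causality calls, which can carry into decisions on adverse drug reactions, SUSARs and late related serious events.

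The documents do not support saying that the causality rule as a whole is inverted, or that related-event counts and SUSAR decisions are bound to be wrong, because the governing definition is correct and judgment is left to the investigator. The size cannot be quantified from the protocol. The primary fatigue analysis and the other efficacy results are unaffected, and the summary table of analyses names no related-event count. The conclusion assumes only that the text shown is the one in force. Whether any entry has actually been misclassified depends on whether sites used this wording, which is not shown.

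**What to change.** Reconcile the two timing bullets in section 10.4.2 by amending the first Related bullet so that a compatible temporal association between the event and administration supports Related. Leave the Unrelated timing bullet as it is. While the list is open, rewrite the mechanism bullet as a statement.

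Notify sites of the correction, and confirm which wording they have been using, in Portuguese or in English. Section 3.3.2 shows that at least 100 participants had been recruited, so causality entries may already exist. If sites used the present wording, check those entries once, without reference to treatment allocation, giving priority to serious events and to any call that was justified by timing.

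The cost is one sentence in an amendment, with the Steering Committee and regulatory or ethics approval that section 16.2 requires, a short notice to sites and, if needed, a one-time check. No change to the design, sample size or efficacy analysis is involved.
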